8.3.3 Management of gastrointestinal hemorrhage

Gastrointestinal hemorrhage, including fecal occult blood (++) and above, hematemesis or bloody stool, should be given active symptomatic treatment. Patients with upper gastrointestinal hemorrhage should be fasted and given acid suppression, gastric mucosal protection, hemostasis (transamin, reptilase, etc.), as well as octreotide if necessary; patients with lower gastrointestinal hemorrhage should be given hemostasis, blood transfusion and supportive care, etc.; for those whose bleeding cannot be controlled, assistance from the surgery department should be requested.

8.3.4 Suggestions for the treatment of proteinuria

For those with two consecutive episodes of urine protein (++) , a 24 h urine protein test is required.

Table 11. Suggested treatments for proteinuria

UPC < 3 g	Treatment is continued at the same dose level and the patient is monitored as clinically indicated
UPC ≥ 3 g	Step 1: Obtain 24-h urine protein Step 2: If the 24-h urine protein is < 3 g, the subject can continue the treatment at the same dose level; If the 24-h urine protein is ≥ 3 g, interrupt the treatment until UPC returns to < 3 g, and then resume the treatment at a lower dose, and monitor the UPC throughout the entire subsequent treatment. If UPC is ≥ 3 g, obtain 24-h urine protein. Step 3: If the 24-h urine protein is still ≥ 3 g after repeated dose reductions, discontinue the trial and follow up the subject according to the protocol.

Note: In case of nephrotic syndrome, the treatment with the investigational drug should be discontinued and the subject should withdraw from the clinical trial.

8.3.5 Interstitial pulmonary fibrosis

The clinical physicians should fully understand the conditions of subjects and be familiar with the drugs that may lead to pulmonary toxicity. The clinical symptoms of the patients and their changes in chest X-ray or CT should be monitored closely. Once a patient shows acute lung symptoms of cough, chest tightness, labored breathing, dyspnea, and hemoptysis of unknown causes, the investigational drug should be interrupted immediately to promptly identify the cause of the symptoms and exclude other causes (such as infection and heart failure). It is recommended to add a chest CT imaging examination, etc. Alveolar lavage fluid analysis and surgical lung biopsy are important means to diagnose interstitial lung disease. Currently, no therapy yields a satisfactory result against pulmonary fibrosis, and correction of hypoxemia and timely administration of corticosteroids are recommended following "Guidelines for Diagnosis and Treatment of Idiopathic Pulmonary (Interstitial) Fibrosis (draft)" issued by the Chinese Medical Association Respiratory Diseases Branch.

Note: The suggestions for the symptomatic treatments of above adverse events are for reference only. For specific countermeasures, please consult a specialist.

9 STUDY PROCEDURES

9.1 Screening Period (from signing informed consent form to obtaining random numbers)

Subjects must sign the informed consent form before undergoing any screening procedures.

Unless otherwise stated, the following screening procedures should be completed within 21 days prior to randomization.

- Patients sign the informed consent form.
- Collection of medical history, including past treatment history, current medical history, drug allergies, and concurrent diseases.
- Physical examination, height, weight, and vital signs (body temperature, blood pressure, heart rate, and respiratory rate).
- Chest x-ray, not required if the subject have undergone chest CT.
- CT or MRI of the chest, abdomen, pelvis and other relevant lesions.
- Brain CT/MRI, required for clinically suspected metastases to the central nervous system only.
- Bone scan, required for clinically suspected bone metastasis only.
- Test of hepatitis B and hepatitis C markers, and HBV DNA.
- Test of serum AFP.

The following information should be collected within 7 days before randomization:

- ECOG PS.
- Hematology, urinalysis, and routine stool test.
- Hepatic and renal function (total bilirubin, direct bilirubin, indirect bilirubin, ALT, AST, AKP, r-GT, LDH, total protein, albumin, blood urea nitrogen, creatinine, uric acid).
- Electrolytes (potassium, sodium, chlorine, calcium, phosphorus).
- Coagulation function (PT or INR).
- Pregnancy test (serum or urine, only for women of childbearing potential).
- Echocardiography (mainly to observe LVEF).
- 12-Lead ECG (the QTc interval must be indicated), for 3 times with about 5 minutes apart.
- Quality of life score (EORTC QLQ-C30 and HCC18).
- Randomization should be carried out after all screening evaluations are completed.

9.2 Treatment Period

- Check the blood pressure once a week post-administration. If the blood pressure is abnormal, follow up with the blood pressure every day, and check the blood pressure three times a week for two cycles after the blood pressure returns to normal, and once a week thereafter.
- Within the first two cycles of administration, carry out the following examinations every two weeks (± 3 days, except for statutory holidays): hematology, urinalysis (not required for female subjects during their menstrual period), hepatic and renal function, and electrolytes. From Cycle 3, the examination is carried out once only at the end of each cycle (± 3 days, except for statutory holidays).
- Within the first three cycles of administration, a 12-Lead ECG is carried out at the end of each cycle (± 3 days, except for statutory holidays), and then carried out at the end of every two cycles (± 7 days, except for statutory holidays). Each examination is carried out after administration for 3 times with about 5 min apart and QTc interval indicated. If there are symptoms such as precordial pain and palpitations, the myocardial zymogram (creatinine kinase, lactate dehydrogenase) should be tested immediately, and ECG should be performed at any time. For clinically significant ECG abnormalities, echocardiography (LVEF) should be performed.
- Physical examination, vital signs, PS score, and coagulation function tests are performed every cycle (± 3 days, except for statutory holidays).
- CT or MRI examination and objective efficacy evaluation of tumor are performed once at the end of every two cycles (± 7 days, except for statutory holidays). If the efficacy reaches CR, PR or SD, the subject must be reexamined 4 weeks after the first evaluation.

Note: For subjects who withdraw from the trial due to unacceptable toxicity, the efficacy evaluation should be conducted upon withdrawal if the efficacy evaluation is not carried out within 4 weeks before withdrawal. Thereafter, the imaging examination is performed at the same frequency, i.e., every 2 cycles until PD or use of other anti-tumor treatments. The radiographic evidence of PD of these subjects must be obtained.

- The quality of life score must be evaluated before each objective efficacy evaluation of tumor.
- Serum AFP is tested once at the end of Cycle 2 (± 7 days, except for statutory holidays) and at the end of Cycle 5 (± 7 days, except for statutory holidays). There is no strict requirement after Cycle 5.
- If patients have abnormal stools such as hematochezia or melena, the fecal occult blood examination should be performed.
- AEs should be observed and recorded frequently.

9.3 Follow-Ups

9.3.1 28-day follow-up after the end of treatment

All subjects should continue safety evaluation within 28 days after the last dose. During the follow-up visit on D28 (\pm 3 days, except for statutory holidays) after the end of treatment, physical examination, vital signs, ECOG PS, hematology, and hepatic and renal function tests should be carried out, and adverse events, concomitant medication and concomitant treatment should be evaluated.

9.3.2 Follow-up of AEs

Adverse events that have not resolved after discontinuing apatinib treatment should be followed and a final evaluation should be made. The follow-up of adverse events ends on D28 after treatment discontinuation.

9.3.3 Survival follow-up

After the 28-day safety follow-up, the subject, his/her family members or local physicians should be interviewed by telephone once a month to collect survival (date and cause of death) and post-treatment information (including received treatments) until the death endpoint, lost to follow-up, or study termination by Hengrui. Each survival follow-up should be documented in the follow-up form in detail.

10 EFFICACY EVALUATION

10.1 Primary Endpoint and Observation Method

Overall survival (OS):

Defined as the time from the date of randomization to death from any cause.

10.2 Secondary Endpoints and Observation Methods

- PFS

PFS is defined as the time from randomization until the date of documented progression or death from any cause, whichever occurs first.

The PFS is assessed as per RECIST 1.1. The analysis of this endpoint includes all tumor assessments during the treatment period and the follow-up period. If the patient has several endpoints that can all be evaluated as PD, then use the first documented PD when analyzing PFS. The study endpoint also includes relapse, the occurrence of new lesions, and death. The initiation of other systemic or targeted anti-tumor treatment is also considered disease progression.

- 3-, 6-, and 12-month PFS rates

Refer to the proportions of evaluable patients without disease progression from the start of the trial to 3, 6, and 12 months.

- Time to progression (TTP)

Refers to the time from randomization to any documentation of radiologic progression.

The PFS is assessed as per RECIST 1.1. The analysis of this endpoint includes all tumor assessments during the treatment period and the follow-up period.

- Objective response rate (ORR)

Refers to the proportion of patients who achieve tumor shrinkage to a certain volume and maintain for a certain period of time, including CR and PR. Objective response is evaluated based on RECIST 1.1. Subjects must have measurable lesions at baseline. The tumor can be assessed as complete response (CR), partial response (PR), stable disease (SD), and disease progression (PD) according to RECIST 1.1 criteria.

- Disease control rate (DCR);

Refers to the proportion of evaluable patients with confirmed CR, PR, or SD (≥ 4 weeks).

- The percentage of evaluable patients with stable disease (SD) of ≥ 4 weeks (confirmed SD in particular)

- 6- and 12-month mortalities

- Quality of life score (QoL);

In reference with EORTC QLQ-C30 (version 3, Chinese version) and HCC-18. See Appendix 9 for details.

Evaluation method: Observe and score the changes in the clinical symptoms and objective test results of tumor patients before and after treatment. Timing of evaluation: Pre-treatment and at the end of Cycles 2 and 3 of treatment. At the end of every two cycles, the quality of life scale should be recorded and evaluated, and the scores of the various areas of the scale should be recorded in the eCRF according to the requirements in the Appendix.

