## 3.2 Secondary Efficacy Endpoints

- Progression free survival (PFS): the time from the date of randomization to onset of progressive disease (PD) (as per RECIST 1.1) or death, whichever occurs first;
- 3-, 6-, and 12-month PFS rates;
- Time to progression (TTP): the time from the date of randomization to any documentation of radiologic progression (as per RECIST 1.1);
- Duration of response (DOR): the time from the first recording of tumor response to the first recording of objective tumor progression or death of any cause;
- Objective response rate (ORR): the proportion of subjects with confirmed complete response (CR) and partial response (PR) when the objective response is assessed as per RECIST 1.1;

- The proportion of subjects with stable disease (SD) for  $\geq 6$  weeks;
- Disease control rate (DCR): the proportion of subjects with confirmed CR, PR, and SD (for  $\geq 6$  weeks);
- 6- and 12-month survival rates;
- Quality of life score: EORTC QLQ-C30 and HCC18.

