The start and end dates of PFS for events with outcomes:

1: Date of radiographic PD (earliest date of progression of target lesions, non-target lesions, or new lesions) - date of randomization +1;

2: Date of death - date of randomization + 1.

If the above 1 and 2 are both met in the one case, the earliest time is taken.

The start and end dates of PFS for events without outcomes:

1: With imaging examination: date of the last adequate imaging examination - date of randomization + 1, as censored data;

2: Without imaging examination: 1 day (i.e., the date of censorship is the date of randomization), as censored data.

With a new anti-tumor treatment: date of the last imaging examination prior to or onset on starting the new anti-tumor treatment - date of randomization + 1, as censored data.

The start and end dates of PFS for those with an endpoint event but missing 2 or more (at least 18 weeks) imaging examinations:

1: Date of the last imaging examination before event observed - date of randomization +1, as censored data.

For the definition of new anti-tumor treatment, refer to Section 7.6.2.

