### 7.6.2 Other Analyses

To assess the balance of new anti-tumor treatments between groups during the study, new anti-tumor treatments (including systemic treatment and local treatment) are summarized. In addition, the new anti-tumor treatments are classified, and the subgroup analyses of OS are performed. New anti-tumor treatments are classified into chemotherapy, targeted therapy, immunotherapy, and local treatments (TACE, surgery, ablation therapy, and radiotherapy). New anti-tumor treatments do not include traditional Chinese medicine and immunomodulators. Before database locking, classification of new anti-tumor treatments is finally determined and archived.

Other sensitivity analyses of OS include:

- 1) The OS of two groups will be compared by the Wilcoxon test and Max-Combo method.
- 2) The survival time of subjects are censored at the start of new anti-tumor treatments.
- 3) In the OS analysis, some subjects who have received some other types of anti-tumor treatments (which may have a major impact on survival) during the study are excluded, such as subjects with subsequent PD1/PD-L1 treatments will be excluded.
- 4) Rank-preserving structural failure time model (RPSFTM) proposed by Robins and Tsiatis: The OS of subjects who have received apatinib (or other targeted therapies) during the study anti-tumor treatment is adjusted using the RPSFTM method. This analysis will be based on the population defined by FAS and the sensitivity analysis method 2), respectively.
- 5) IPCW method proposed by Robins and Finkelstein: Using the IPCW method to analyze the HR between the treatment group and control group, with reference to relevant medical literature, the baseline variables and time-related variables are planned to be considered in the IPCW model including ECOG PS, age, gender, presence of extrahepatic metastasis, number of line(s) of past treatment, BCLC grade, etc. If necessary, the duration of study drug exposure, and liver function parameters (such as ALT, AST, and bilirubin) may also be included. The bootstrap method is used to sample from the treatment group and control group, and the 95% CI of the HR is estimated.

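### New therapy before progression is a PFS event in protocol 10.2 but is censored in the SAP, and the only written TTP censoring rule carries an exception that can override it

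*Protocol*

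**What the plan says.** **New therapy and PFS.** After listing what counts towards PFS, protocol 10.2 adds: "The initiation of other systemic or targeted anti-tumor treatment is also considered disease progression". Protocol 2.3 has no such event; it names progression or death. SAP 3.2 agrees with 2.3: "the time from the date of randomization to onset of progressive disease (PD) (as per RECIST 1.1) or death, whichever occurs first". SAP 7.1.3 handles new therapy by censoring. The end date is given as "With a new anti-tumor treatment: date of the last imaging examination prior to or onset on starting the new anti-tumor treatment", and the record is marked as censored. The same section adds: "For the definition of new anti-tumor treatment, refer to Section 7.6.2". In SAP 7.6.2, "new anti-tumor treatments (including systemic treatment and local treatment) are summarized". The classes named there are chemotherapy, targeted therapy, immunotherapy and local treatments (TACE, surgery, ablation, radiotherapy). It also states: "New anti-tumor treatments do not include traditional Chinese medicine and immunomodulators".

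**Patients without an event.** Protocol 12.3 dates PFS and TTP at the last radiographic assessment up to the cutoff. It then makes an exception for any RECIST assessment that shows no progression, and uses the data cutoff instead. (The English text says *reviewed* where *censored* appears to be meant.) For PFS, SAP 7.1.3 has no such exception: "date of the last adequate imaging examination - date of randomization + 1, as censored data". It writes out formulas for OS and PFS but none for TTP. SAP 7.3.2 refers TTP only to the general principles.

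**The concern.** The same patient is an event under one document and censored under the other, and the set of treatments that triggers the rule also differs. Neither document says which prevails or why the rule changed. If this is left open, a choice between PFS definitions could be made after results are seen.

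The exception in protocol 12.3 raises a different problem. Scanned patients without progression normally have a scan showing none, so the exception, read literally, reaches nearly everyone the last-scan rule was written for. It would count time without scans as progression-free time. This matters most for TTP, because death is not a TTP event and no other text names a TTP censoring date.

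**Working it through.** **1. The rules side by side.** Take a patient with a clean scan at week 8 who starts another treatment at week 10, before progression.

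| Treatment started | Protocol 10.2 | Protocol 2.3, SAP 3.2 | SAP 7.1.3 with 7.6.2 |
|---|---|---|---|
| Systemic or targeted | Event, week 10 | Not an event | Censored, week 8 |
| Local (e.g. TACE) | Not named, so no event | Not an event | Censored, week 8 |
| Chinese medicine or immunomodulator | Unclear (may be systemic) | Not an event | Not new therapy, stays at risk |

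The last row adds little, because protocol 8.1.3 prohibits approved Chinese medicine preparations for liver cancer and immunomodulators during the trial. The SAP line follows the list for patients without an outcome, so it is also unclear whether it overrides a later progression or death. It conflicts with 10.2 on either reading.

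**2. Reach.** SAP 7.3.2 estimates the 3-, 6- and 12-month PFS rates by Kaplan-Meier, so they inherit the PFS rule. It also ties the end of response in DOR to the PFS progression date. OS does not use any of this.

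**3. Size for PFS (illustrative).** Neither document gives a PFS figure to reproduce, or the share of patients starting new therapy before progression. Trials were simulated.
- From the documents: 390 patients at 2:1; OS medians 8.5 and 6 months and 12-month accrual (protocol 4.3); cutoff at the 312th death (12.3); scans at weeks 8 and 12, then every 8 weeks.
- Assumed: exponential times; progression medians 2.4 and 1.44 months; correlation 0.5 between progression and death; new therapy at 20–100% of the patient's own time to progression or death, with scanning ending then.

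| Use, both arms | HR, event rule | HR, censor rule | Shift | Events |
|---|---|---|---|---|
| 3% | 0.691 | 0.687 | 0.004 | – |
| 5% | 0.691 | 0.683 | 0.008 | 388 v 368 |
| 10% | 0.695 | 0.680 | 0.015 | 388 v 349 |

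The event counts are as expected: 388 − 368 = 20 against 5% × 390 = 19.5, and 388 − 349 = 39 = 10% × 390. At 5% use the apatinib median is 2.6 v 2.7 months. The log-HR shift there is ln(0.691/0.683) = 0.012, against a standard error near √[1/(388 × 2/3 × 1/3)] = 0.108.

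With scans spread over the ±7-day window and Efron ties, the shifts are 0.636 − 0.627 = 0.009 at 5% and 0.641 − 0.621 = 0.020 at 10%. The absolute HRs depend on these choices; the shifts hardly do.

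Unequal use gives larger gaps in either direction: apatinib/placebo 5%/10% gives 0.668 v 0.694, and 10%/5% gives 0.719 v 0.672. A separate set-up with progression medians 4.5 and 2.0 months and a constant 0.02 per month start rate (13% and 7.4% of patients) gave 0.557 v 0.523.

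**4. What the exception does to a date.** For a patient still scanned on schedule, moving from last scan to cutoff adds up to 2 × 28 = 56 days, or 56/30.4375 = 1.8 months. For a patient whose scans stopped early, it adds all the time to cutoff.

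**5. Size for TTP (illustrative).** The base assumptions are the same. The 15% loss of protocol 4.3 is spread uniformly over each patient's time to death.

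| Loss | Last scan | Cutoff, not past death | Cutoff, carried past death |
|---|---|---|---|
| None | 0.675 | 0.675 | 0.729 |
| 5% | 0.677 | 0.690 | 0.738 |
| 15% | 0.674 | 0.704 | 0.739 |

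With no loss the first two columns agree: a patient who dies between scans is absent from the next scan's risk set either way. With loss, patients who left without progression are carried forward as progression-free, and the HR moves by 0.704 − 0.674 = 0.030. With spread scan dates and Efron ties the 15% figures are 0.598 and 0.638.

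**The case against.** The SAP gives one explicit PFS formula, and three places (protocol 2.3, SAP 3.2, SAP 7.1.3) leave new therapy out as an event. Analysts would follow the SAP, and 10.2 is a single stray sentence. That stands, and it limits the PFS part to an unexplained departure from the protocol on secondary endpoints.

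New therapy before progression may also be rare. Protocol 4.6 prohibits it, and the wording in 4.6 and 9.2 about scanning until other treatment starts covers only patients who withdrew for toxicity. That stands too. A reader might infer from the unequal-use figures that the PFS result could be moved materially in either direction, but no document supports unequal use or a rate as high as 10%.

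The exception in 12.3 may be harmless in intent. The OS rule in the same paragraph uses the cutoff date when later data settle a patient's status, and the PFS/TTP clause may be the same device for a clean scan taken after the cutoff. On that reading the last-scan rule survives. The clause does not say so, however. It applies to any scan without progression.

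Finally, SAP 7.3.2 sends TTP to the general principles, which contain 7.1.3, so last-scan censoring can be inferred. It remains an inference, because the only formulas written there are for OS and PFS.

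**Conclusion.** Both parts hold on the text. The PFS conflict is real in rule and in scope, and the PFS to be reported is not that of protocol 10.2. Its likely numerical effect is small: under 0.01 on the HR at 5% use and about 0.01–0.02 at 10%, on assumed usage equal in both arms. The exception in 12.3 is defective as worded. The SAP replaces it for PFS, but for TTP protocol 12.3 remains the only explicit censoring rule. The literal reading biases TTP by about 0.03 on the HR with 15% loss and dates stopped at death, and not at all with no loss. It rests on treating the sample-size loss allowance as loss during scanning.

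Three stronger readings are not supported:
- That the primary conclusion is at risk. OS, the 312-death trigger and the sample size do not depend on these rules.
- That TTP would shift to 0.729 or beyond. This requires keeping patients at risk after death.
- That the SAP rule on missed scans is a further contradiction. The protocol is silent there, so the SAP adds to it.

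**What to change.** Before unblinding:

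1. State one PFS rule for new anti-tumor therapy in both documents. Either rule could serve, but 10.2 is the outlier, so align it to the SAP's censoring and report new therapy counted as an event as a named sensitivity analysis. State whether the censoring overrides a later progression or death.
2. Use one definition of new anti-tumor treatment. SAP 7.6.2 lists radiotherapy without qualification, while protocol 8.2 allows small-area palliative radiotherapy for bone metastases during study medication. Reconcile the two before the definition drives PFS censoring, or protocol-permitted care would end a patient's PFS follow-up.
3. In protocol 12.3, delete the exception, or limit it expressly to assessments after the cutoff that show no progression.
4. Add one line to SAP 7.1.3: TTP is censored at the last adequate imaging on or before the cutoff, including for deaths without radiographic progression.

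The cost is wording in protocol 10.2 and 12.3 (reported to the ethics committee, as protocol 15 requires), the matching SAP text and one extra PFS run. No new data are needed.
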